## **6 DOSE MODIFICATIONS**

Dose reductions or dose escalations are not permitted. Dose delays due to adverse events are not permitted. If an AE occurs causing a missed dose, the subject will stop the nivolumab administration schedule and proceed to surgery. Dose delays for other reasons are allowed with prior approval from the Sponsor-Investigator.

### **6.1 MANAGEMENT ALGORITHMS**

Immuno-oncology agents are associated with AEs that can differ in severity and duration than AEs caused by other therapeutic classes. Nivolumab is considered an immuno-oncology agent in this protocol. Early recognition and management of AEs associated with immuno-oncology agents may mitigate severe toxicity.

Management algorithms have been developed to assist investigators in assessing and managing the following groups of AEs: Gastrointestinal, Renal, Pulmonary, Hepatic, Endocrinopathies, Skin, Neurological.

For subjects expected to require more than 4 weeks of corticosteroids or other immunosuppressants to manage an AE, consider recommendations provided in the algorithms. These algorithms can be referenced in the Nivolumab IB. The guidance provided in these algorithms should not replace the Investigator's medical judgment but should complement it.

### **6.2 DISCONTINUATION CRITERIA**

Subjects may discontinue study treatment at any time. Subjects may be removed from study for any of the following reasons:

- Radiographic disease progression that is not amendable to resection
- Clinical disease progression that would not benefit from surgery
- Inter-current illness that would, in the judgment of the investigator, affect assessments of clinical status to a significant degree or require discontinuation of study drugs
- Completion of protocol treatment.
- Death
- Subject non-compliance
- Treatment should be permanently discontinued for the following:
  - Any Grade 2 drug-related uveitis or eye pain or blurred vision that does not respond to topical therapy and does not improve to Grade 1 severity within the re-treatment period OR requires systemic treatment
  - Any Grade 3 non-skin, drug-related adverse event lasting > 7 days, with the following exceptions for drug-related laboratory abnormalities, uveitis, pneumonitis, bronchospasm, hypersensitivity reactions, infusion reactions, and endocrinopathies:
    - Grade 3 drug-related uveitis, pneumonitis, bronchospasm, hypersensitivity reaction, or infusion reaction of any duration requires discontinuation
    - Grade 3 drug-related endocrinopathies adequately controlled with only physiologic hormone replacement **do not** require discontinuation

- Grade 3 drug-related laboratory abnormalities **do not** require treatment discontinuation except those noted below
  - Grade 3 drug-related thrombocytopenia > 7 days or associated with bleeding requires discontinuation
  - Any drug-related LFT abnormality that meets the following criteria require discontinuation:
    - AST or ALT > 8 x ULN
    - Total bilirubin > 5 x ULN
    - Concurrent AST or ALT > 3 x ULN and total bilirubin > 2 x ULN
- Any Grade 4 drug-related adverse event or laboratory abnormality, except for the following events which **do not** require discontinuation:
  - Isolated Grade 4 amylase or lipase abnormalities that are not associated with symptoms or clinical manifestations of pancreatitis and decrease to < Grade 4 within 1 week of onset.
  - Isolated Grade 4 electrolyte imbalances/abnormalities that are not associated with clinical sequelae and are corrected with supplementation/appropriate management within 72 hours of their onset
  - Grade 4 lymphopenia or leukopenia
  - Grade 4 drug-related endocrinopathy adverse events, such as adrenal insufficiency, ACTH deficiency, hyper- or hypothyroidism, or glucose intolerance, which resolve or are adequately controlled with physiologic hormone replacement (corticosteroids, thyroid hormones) or glucose-controlling agents, respectively, may not require discontinuation after discussion with and approval from the Principal Investigator.

## 7 **CONCOMITANT THERAPY**

### **7.1 PERMITTED MEDICATIONS – USE WITH CAUTION**

As there is potential for hepatic toxicity with nivolumab or nivolumab/ipilimumab combinations, drugs with a predisposition to hepatotoxicity should be used with caution in patients treated with nivolumab-containing regimen.

Subjects are permitted to use topical, ocular, intra-articular, intranasal, and inhalational corticosteroids (with minimal systemic absorption). Physiologic replacement doses of systemic corticosteroids are permitted, even if > 10 mg/day prednisone equivalents. A brief course of corticosteroids for prophylaxis (eg, contrast dye allergy) or for treatment of non-autoimmune conditions (eg, delayed-type hypersensitivity reaction caused by contact allergen) is permitted.

## 8 **STUDY ASSESSMENTS**

### **8.1 GENERAL GUIDELINES**

- Screening evaluations are to be done within 14 days of registration with the following exceptions:

- informed consent, hepatitis B and C testing, and radiographic disease assessments to be done within 28 days of registration
- serum pregnancy test must be done within 24 hours prior to registration
- After registration, subjects should begin study drug within 72 hours.
- On study assessments to be completed +/-3 days, radiographic assessments will be completed within +/- 7 days.

## **8.2 PREGNANCY TEST FOR WOCBP**

A serum pregnancy test is required within 24 hours prior to registration. If day 1 is more than 24 hours after the screening pregnancy test, the pregnancy test must be repeated prior to day 1 of drug administration. A pregnancy test is also required at day 29 and prior to surgery. After discontinuation from nivolumab these should be repeated at approximately 30 days and approximately 70 days.

## **8.3 BASELINE ASSESSMENTS:**

- Medical history will be obtained to capture relevant underlying conditions. The baseline examinations should include weight, height, ECOG Performance Status, BP, HR, temperature, and oxygen saturation by pulse oximetry at rest (also monitor amount of supplemental oxygen if applicable) should be performed within 14 days prior to registration. Concomitant medications will be collected from within 14 days prior to the first dose through the study treatment period.
- Laboratory assessments will be done within 14 days prior to registration and are to include: CBCD, LFTs (ALT, AST, total bilirubin, alkaline phosphatase), BUN or serum urea level, creatinine, calcium, Magnesium, Sodium, Potassium, Chloride, phosphate, LDH, glucose; TSH, free T3, and free T4.
- The following baseline local laboratory assessments to be done within 28 days prior to registration: Hepatitis B and C testing (HBV sAg and HCV Ab or HCV RNA).
- **After patients are entered into this study**, the clinical team will oversee collection of primary tumor biopsy if not previously performed.

## **8.4 RADIOGRAPHIC ASSESSMENT:**

- Initial evaluation will include PET/CT or CT scan of the head and neck to assess local and regional disease extent. PET/CT or CT of the chest, abdomen, and pelvis will also be utilized to assess for distant disease.
- MRIs may be substituted in place of PET/CT or CT scan for clinical reasons such as subject intolerance of intravenous contrast material.
- The same method of assessment (i.e. CT, MRI) and the same technique should be used to characterize each identified and reported lesion at baseline and during follow-up.
- RECIST 1.1 guidelines will be used.
- Restaging scans of the head and neck will be performed following the 3rd cycle between Days 29-36
- If tumor cannot be visualized on radiology exam, caliper measurement should be used.

### **8.5 CLINICAL TUMOR ASSESSMENT:**

- Primary tumors will be assessed for progression using caliper measurement on prior to registration and following the third cycle of treatment Day 29-36. Caliper measurements are only required if tumor cannot be visualized on radiology exam.
- Tumors will be photographed at time of clinical assessment on day 1 and following the third cycle of treatment for a qualitative assessment of possible effects on reduction in tumor size, necrosis, erythema/inflammation, and vascularity. Standard flash or endoscopic digital photography may be used depending on the site and accessibility for photography.
- Following completion of the trial, two blinded head and neck tumor surgeons (Photograph Examiner #1 and #2) will review the photographs separately. Each examiner will record estimated size, percent increase or decrease, and anatomic descriptive terms related to change in size, shape, texture, and color over time from the photographs.

### **8.6 ON STUDY ASSESSMENTS**

- Toxicity assessments will be continuous during the treatment phase. Adverse events and laboratory values will be graded according to the NCI-CTCAE version 4.03.
- On-study weight, ECOG performance status, and vital signs should be assessed at each on-study visit prior to dosing. Vital signs should also be taken as per institutional standard of care. Oxygen saturation by pulse oximetry at rest (also monitor amount of supplemental oxygen if applicable) should be assessed at each on-study visit prior to dosing. The start and stop time of the study therapy infusions should be documented.
- Physical examinations are to be performed as clinically indicated. If there are any new or worsening clinically significant changes since the last exam, the changes should be reported as AEs.
- Laboratory testing prior to each dose: Within 72 hours prior to re-dosing to include CBCD, LFTs, BUN or serum urea level, creatinine, Ca, Mg, Na, K, Cl, LDH, Glucose, amylase, lipase.
- Thyroid function testing should be done every 6 weeks (every 3 cycles) for subjects receiving nivolumab.
- A minimum of five and a maximum of seven 5-mL tubes of peripheral blood will be collected for correlative studies. See section 12 for more details.
- Additional measures, including non-study required laboratory tests, should be performed as clinically indicated or to comply with local regulations. Laboratory toxicities (eg, suspected drug induced liver enzyme evaluations) will be monitored during the follow-up phase via on site/local labs until all study drug related toxicities resolve, return to baseline, or are deemed irreversible.
- If a subject shows changes on pulse oximetry or other pulmonary-related signs (hypoxia, fever) or symptoms (eg. dyspnea, cough, fever) consistent with possible pulmonary-related signs (hypoxia, fever) or symptoms (eg, dyspnea, cough, fever) consistent with

possible pulmonary adverse events, the subject should be immediately evaluated to rule out pulmonary toxicity.

- **At the time of surgery**, portions of the excised HNSCC tissues that are not required for clinical purposes (existing material) will be used for correlative research. See section 12 for more details.
- Some of the assessments referred to in this section may not be captured as data in the eCRF. They are intended to be used as safety monitoring by the treating physician. Additional testing or assessments may be performed as clinically necessary or where required by institutional or local regulations.

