### **5 STUDY INTERVENTION**

#### **5.1 NIVOLUMAB ADMINISTRATION**

Nivolumab will be given every two weeks at a dose of 3mg/kg will be administered as a 60 minute IV infusion (+/- 10 minutes). Study drug will be administered on an outpatient basis. Subjects may be dosed no less than 12 days from the previous dose of drug.

REGIMEN DESCRIPTION			
Agent	Dose	Route	Schedule
Nivolumab	3mg/kg	IV	Cycle 1 = Day 1 Cycle 2 = Day 15 Cycle 3 = Day 29  Response assessment

		Cycle 4 = Day 43 if stable disease or response after day 29.
--	--	--

The dosing calculations should be based on the actual body weight at baseline. If the subject's weight on the day of dosing differs by > 10% from the weight used to calculate the original dose, the dose must be recalculated. All doses should be rounded to the nearest milligram. **There will be no dose reductions allowed.**

Nivolumab injection is to be administered as an IV infusion through a 0.2-micron to 1.2-micron pore size, low-protein binding polyethersulfone membrane in-line filter at the protocol-specified doses. It is not to be administered as an IV push or bolus injection. Nivolumab injection can be infused undiluted (10 mg/mL) or diluted with 0.9% Sodium Chloride Injection, USP or 5% Dextrose Injection (USP to protein concentrations as low as 1 mg/mL). Care must be taken to assure sterility of the prepared solution as the product does not contain any antimicrobial preservative or bacteriostatic agent.

Subjects should be carefully monitored for infusion reactions during nivolumab administration. If an acute infusion reaction is noted, subjects should be managed according to Protocol Section 5.3.

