## 5.2 SURGICAL RESECTION

Between days 28-35, subjects will be evaluated for disease progression through clinical and radiographic tumor assessment, and for toxicity by history, physical and clinical labs. In the event of disease progression, subjects will proceed to definitive surgical resection between days 36-42 and no later than 50 days after randomization. If disease is stable or response is observed, subjects will have the fourth administration of nivolumab on Day 43 (+/- 1 day) followed by definitive surgical resection on day 50-56 and no later than 60 days randomization.

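### Patients who receive the Day 43 dose have no scheduled safety labs after it, so new silent laboratory toxicity before and after surgery is not systematically looked for

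*Combined protocol and SAP*

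**What the plan says.** Section 8.6 sets the safety panel (blood count, liver and renal tests, electrolytes, LDH, glucose, amylase, lipase) with the words "Laboratory testing prior to each dose: Within 72 hours prior to re-dosing". The Study Calendar (8.9) agrees: its blood count and chemistry, magnesium and phosphate, and LDH, amylase and lipase rows are marked at screening and on Days 1, 15, 29 and 43, with no mark at surgery or in follow-up. For thyroid tests, 8.6 says "Thyroid function testing should be done every 6 weeks (every 3 cycles) for subjects receiving nivolumab"; the calendar marks screening, Day 1 and Day 43.

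The last dose depends on response. Section 5.1 gives "Cycle 4 = Day 43 if stable disease or response after day 29". Under 5.2, progressors have surgery on Days 36-42 after dose 3, and all others on Days 50-56 after dose 4. Between Days 28 and 35, 5.2 also requires evaluation "for toxicity by history, physical and clinical labs". Patients who miss a dose because of toxicity come under Section 6: "If an AE occurs causing a missed dose, the subject will stop the nivolumab administration schedule and proceed to surgery".

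Sections 10.4 and 11.4 count adverse events to 6 weeks after surgery, and 8.7-8.8 allow them to be reported by telephone. Section 8.6 also has laboratory toxicities followed by local labs until they resolve, return to baseline or are judged irreversible, and allows further tests when clinically indicated.

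**The concern.** The adverse-event window runs well past the last scheduled panel, and some events in it can be seen only in a blood sample. Potential drug-induced liver injury is defined in 13.2 by ALT or AST above 3 times and bilirubin above 2 times the upper limit of normal. It must be reported as an SAE, and 13.3 collects SAEs for 100 days after dosing stops. A telephone call cannot find an asymptomatic transaminase or lipase rise.

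Where the protocol wants a blood test late in the course, it schedules one. On pregnancy testing, 8.2 says "A pregnancy test is also required at day 29 and prior to surgery", and it repeats the test at about 30 and 70 days. Nothing comparable exists for the safety panel.

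Two things are at stake. A four-dose patient may go to major surgery with no scheduled laboratory check after the last dose. A silent grade 3-4 laboratory event after the last panel would also enter the safety tables, and the 11.4 stopping rule, as no event. Any bias is toward under-counting.

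**Working it through.** The plan states no figure on this point to reproduce. The check is day arithmetic from Day 1, using planned surgery windows.

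**Inputs.** Panel up to 72 hours (3 days) before a dose (8.6); doses may move by 1 day (5.2, calendar note g); surgery on Days 50-56 or 36-42 (5.2); window ends 42 days after surgery (10.4, 11.4). The general rule in 8.1, "On study assessments to be completed +/-3 days", does not move the panel past the dose, because 8.6 requires it beforehand.

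**Four-dose patients**
- Dose 4: Days 42-44. Panel: Day 42 - 3 = 39 at the earliest, Day 44 at the latest.
- Age of panel at surgery: 50 - 44 = 6 days to 56 - 39 = 17 days.
- End of window: 50 + 42 = Day 92 to 56 + 42 = Day 98.
- Days in the window after a Day 43 dose: 92 - 43 = 49 to 98 - 43 = 55. With the one-day window: 92 - 44 = 48 to 98 - 42 = 56.
- Scheduled safety panels in that time: none.

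**Progressors (last dose on nominal Day 29)**
- The 5.2 labs span 8 days. Seven (Days 29-35) fall on or after the dose 3 day, and six (Days 30-35) strictly after it.
- A draw on Day 28, or before the infusion on Day 29, can meet both 5.2 and 8.6 and yet precede dose 3. Section 5.2 does not list the tests.
- If drawn on Days 30-35, these labs are 36 - 35 = 1 to 42 - 30 = 12 days old at surgery.
- The window ends on Days 78-84, which is 49-55 days after dose 3. Even with labs on Day 35, 78 - 35 = 43 to 84 - 35 = 49 days follow with no scheduled panel.
- The six-week thyroid test is due on Day 43, or Days 40-46 with the 3-day window. Four of the seven planned progressor surgery days (36-39) come before it.

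**Patients who stop early for an adverse event.** The known toxicity is followed under 8.6 and 13.5. With no further dose, nothing triggers another scheduled full panel.

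**Sensitivity of the stopping rule.** The 11.4 likelihood ratio for x events in n patients is (0.25/0.05)^x × (0.75/0.95)^(n-x).
- 2 of 9 gives 4.78 (stop), as printed; 1 of 9 gives 0.75 (continue).
- 3 of 17 gives 4.57 (stop), as printed; 2 of 17 gives 0.72 (continue).

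One missed event can change the decision. This does not show that such misses are common.

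**The case against.** **A check before surgery already exists.** For progressors this largely stands. Section 5.1 puts response assessment after cycle 3, 8.4 and 8.5 put restaging on Days 29-36, and most of the 5.2 window follows dose 3. A reader might infer that every patient reaches surgery unchecked after the last dose; the documents do not support that. For four-dose patients, however, the 5.2 labs precede dose 4.

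**Follow-up labs are provided for.** A reader might infer that laboratory toxicity is unmonitored after dosing. That is also unsupported: 8.6 follows it to resolution, and 13.5 requires clinically significant results to be reported for at least 100 days after the last dose. But these provisions act on toxicity that is known or suspected, or on results already obtained. They do not order a test in a patient without symptoms. Routine pre-operative labs probably happen, but the protocol neither requires them nor says which tests they contain.

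**The remedy covers little of the window and may cause stopping.** Both parts have some force. Even a draw on the day of surgery leaves 42 of 48-56 days, at least 75%, uncovered. Section 11.4 also has no exemption for isolated laboratory values, whereas 6.2 tolerates most grade 3 laboratory abnormalities and some transient grade 4 ones. Applying the printed boundaries after each patient from the third to the nineteenth, with exact binomial probabilities, the chance of stopping is 9% at a recorded grade 3-4 rate of 5% and 31% at an assumed 10%. That cost should be known in advance. It comes from the rule working on fuller data and is no reason to leave the events unlooked for.

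**Conclusion.** The point holds as a minor design gap. It is definite for four-dose patients, possible for progressors, and present for early stoppers only as regards toxicity other than the one already being followed.

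A reader might go further and infer that the grade 3-4 rate or the stopping rule is materially biased. The documents give no rate of silent laboratory events and no detection rate, so neither the size of the under-count nor its effect on stopping can be derived. Assuming that some fraction of all grade 3-4 events is missed would not measure this gap, which concerns only new, silent, late laboratory events. The primary pathological endpoint is unaffected.

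The day counts rest on planned surgery dates. They also rest on reading the 5.2 clinical labs as an unspecified panel that can be drawn on any day of its window.

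**What to change.** Add to 8.6, and mark in the calendar:

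> The pre-dose panel plus TSH, free T3 and free T4 will be drawn at the pre-surgical blood draw (Section 12), after the last nivolumab dose and early enough for results to be reviewed before surgery, in every treated subject who goes to surgery. For progressors, 5.2 labs drawn after dose 3 with the same panel may serve. Results will be entered in the eCRF and graded by CTCAE 4.03.

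The eCRF sentence is needed because 8.6 says "Some of the assessments referred to in this section may not be captured as data in the eCRF".

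The cost is at most 19 extra panels, at a draw that Section 12 already requires, plus data entry. The recorded grade 3-4 rate may be slightly higher, and it feeds the 11.4 stopping rule. The change does not cover treated patients who never reach surgery, and the 6 weeks after surgery would still rest on clinically indicated labs.

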## **8.7 OFF STUDY AND FOLLOW UP**

**8.8 SUBJECTS WILL BE FOLLOWED EVERY 3 MONTHS (+/- 15 DAYS) FROM THE DATE OF SURGERY UNTIL PROGRESSION OR UNTIL DEATH, WHICHEVER COMES FIRST, FOR A MAXIMUM OF 12 MONTHS AFTER THE LAST SUBJECT HAS BEEN REGISTERED TO THE TRIAL. AES WILL BE RECORDED FOR 6 WEEKS AFTER SURGERY. AES CAN BE REPORTED THROUGH REGULAR CLINIC VISITS OR OVER THE PHONE.**

## 8.9 STUDY CALENDAR

Activity	Screening			Patient Registration	Nivolumab Administration g		If stable or response only:	Surgery c, h	Follow Up					
	Within 28 days of Registration	Within 14 days of Registration	Within 24 hours of registration		Day 1 i	Day 15	Day 29		Day 43 c	Day 36-42 or Day 50-56	30 days d	42 days j	70 days d	Q 3 months b
Informed consent	X													
History and Physical examination		X			X a	X a	X a	X a						
ECOG PS		X			X	X	X	X						
Vital signs, weight		X			X	X	X	X						
CBCD & CMP		X			X	X	X	X						
Mag, Phos		X			X	X	X	X						
HVB and HVC screening	X													
TSH, free T3, free T4		X			X			X						
LDH, amylase, lipase		X			X	X	X	X						
Serum Pregnancy test (WOCBP only)			X				X		X	X		X		
Assessment of Concomitant medications		X			X			X						
Adverse events assessment					X			X						
Tumor Photographs k					X									
Radiographic or Caliper Measurement	X													
Tumor Assessment k														
Survival Status and Disease Status b													X	
Nivolumab Administration				Nivolumab Administration	X	X	X	X						
Surgery										X				
Tumor biopsy	Any time after consent and prior to day 1 dose									X				
Research blood collection f	Any time after consent and prior to day 1 dose									X				

- a. Performed as clinically indicated
- b. Follow up every three months (+/- 15 days) from the time of surgery until progression or death, for up to 12 months after the last subject has been registered to the trial.
- c. If disease is stable or response is observed at days 28-35, subjects will have the forth administration of nivolumab on Day 43, followed by definitive surgical resection on day 50-56.
- d. Serum pregnancy test to be done 30 days and 70 days after last drug administration.
- e. AEs will be recorded for 6 weeks after surgery.

Protocol version 6 dated December 6, 2019

- f. A minimum of five and a maximum of seven, 5-mL tubes of peripheral blood will be collected for correlative research in purple top tubes. See section 12 for more details about tumor biopsy and research blood collection.
- g. Nivolumab may be administered +/- 1 day
- h. Surgery is to be performed any time between Days 36-42 for patients whose disease has progressed and no later than 50 days after randomization or between Days 50-56 for patients who have stable disease or response, with surgery to be no later than 60 days after randomization.
- i. Screening labs done within 72 hours of day 1 do not need to be repeated.
- a. AEs will be assessed up to 6 weeks after surgery and may be assessed through clinic notes and/or reported via phone.
- b. See section [8.5 Clinical Tumor Assessment](#) for more information.

